9.7.3. Analysis of treatment data

Descriptive statistics will be calculated for the treatment duration. The following frequencies will be calculated: the number of patients with dose reductions, number of patients with dose interruptions, total number of dose reductions and frequencies of reasons for reduction, total number of dose interruptions and frequencies of reasons for interruption.

9.7.4. Analysis of primary outcome(s)

Descriptive summaries of Kaplan-Meier (KM) estimates (including number of failed, number censored, 25th and 75th percentiles with respective 95% CI and median with 95% CI) and KM curves will be presented for OS.

9.7.5. Analysis of secondary outcome(s)

Descriptive summaries of KM estimates (including number of failed, number censored, 25th and 75th percentiles with respective 95% CI and median with 95% CI) and KM curves will be presented for time-to-event effectiveness variables (TTP, PFS). Summary statistics will be calculated for duration of Stivarga[®] treatment.

Disease control rate, defined as percentage of patients whose best response was not progressive disease (i.e. complete response, partial response or stable disease), and the corresponding 95% confidence interval will be calculated.

Category counts and frequencies (percentages) will be calculated for tumor status at different visits and best overall tumor response.

AEs will be summarized using the MedDRA and the CTCAE coding system. Event rates for single AEs will be calculated based on the total number of patients valid for safety. AEs will be categorized according to relation, seriousness, CTCAE grade (version 4.03), discontinuation of therapy, action taken and outcome. Special attention will be paid to SAEs and unexpected or unlisted ADRs.

The analyses described in this section will be performed on treatment-emergent AE. Events which are not treatment-emergent will be tabulated without further stratification. All patients will be presented with all details from the AE report form. Further details of the safety analysis will be described in the SAP.

Subgroup analyses stratified with prognostic/predictive factors collected at baseline may be explored.

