9.1.2. Secondary endpoint(s)

The secondary endpoints are:

- Progression free survival (PFS) is defined as the time interval measured from the day of start of Stivarga® treatment to diagnosed (radiological or clinical) progression or death, whichever comes first. Progression-free survival for patients without disease progression or death at the time of analysis will be censored at the last date of tumor evaluation.
- Time to progression (TTP) is defined as the time interval from start of Stivarga® therapy to the date of diagnosed (radiological or clinical) progression. Patients without tumor progression at the time of analysis will be censored at their last date of tumor evaluation.
- Disease control rate (DCR) is defined as percentage of patients, whose best response was not progressive disease (i.e. complete response, partial response or stable disease).
- Duration of Stivarga® treatment is defined as the time interval from start of Stivarga® therapy to the date of permanent discontinuation of Stivarga® therapy (regardless of the reason for discontinuation). It will be calculated as last dosing date - first dosing date + 1. A patient with only one dose of Stivarga® will be considered as having a treatment duration of one day.
- The tumor status at different visits will be evaluated according to the categories “complete response”, “partial response”, “stable disease”, “progressive disease by clinical judgment”, “progressive disease measurement proven”, “unknown” and “not applicable”. The best overall response will be analyzed providing absolute and relative frequencies of the tumor status categories.
- Incidence of treatment-emergent adverse events (TEAE) - patients will be monitored for TEAEs using the NCI-CTCAE Version 4.03. Detailed information collected for each TEAE will include: a description of the event, duration, whether the TEAE was serious, relationship to Stivarga®, action taken, clinical outcome. Summary tables will present the number of subjects observed with TEAEs and corresponding percentages. Additional subcategories will be based on event intensity and relationship to study drug.

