9.3.13. Adverse events

New adverse events occurring during the course of study will be documented from the first Stivarga[®] intake until 30 days after end of Stivarga[®] treatment (for further details refer to Section 11.2). Adverse events already documented will be updated with new information during the whole course of the study.

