9.7. Data analysis

9.7.1. Statistical considerations

Statistical analyses will be of explorative and descriptive nature. The study is not aimed to confirm or reject pre-defined hypotheses.

All variables will be analyzed descriptively with appropriate statistical methods: categorical variables by frequency tables (absolute and relative frequencies) and continuous variables by sample statistics (i.e. mean, standard deviation, minimum, median, quartiles and maximum). Continuous variables will be described by absolute value and as change from baseline per analysis time point, if applicable.

Patients receiving at least one dose of Stivarga® will be included in the analysis. Whenever reasonable, data will be stratified by subgroups (e.g. primary site of disease, baseline ECOG, number of prior treatment lines, KRAS mutation at study entry, concomitant diseases of special interest, location of

metastases, age, sex). In particular, the stratification by the number of prior treatment lines (≤ 4 vs > 4) will be performed in order to account for the changed inclusion criteria.

Sample size and disposition information by analysis time point will be displayed in a frequency table.

All issues concerning patient validity, data consistency checks, permissible data modifications will be described in detail in the Data Management Plan. All statistical issues including derived variables for analysis, handling of missing data and proposed format and content of tables will be detailed in the Statistical Analysis Plan (SAP). The SAP will be finalized before study database lock.

It is planned to have two interim analyses: one analysis of the baseline and safety data approximately 1.5 years after start of study or after half the patients have been enrolled, whatever comes earlier, and a second analysis of efficacy and safety data in July 2016. The final analysis will be performed 12 months after last patient last visit.

9.7.2. Analysis of demography, disease details, prior and concomitant medication and other baseline data

Demographic data, baseline characteristics, diagnosis and prior treatment of CRC, concomitant diseases, and concomitant medication will be described with summary statistics such as mean, SD, minimum, 1, 5, 25, 75, 95, 99 percent quantiles, median, maximum, minimum for continuous variables, and category counts and frequencies (percentages) for categorical variables.. Concomitant medication will be coded using WHO's drug dictionary.

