9.7.6. Bias, confounding and effect-modifying factors

In general data collected in this study may suffer from biases (e.g. interviewer bias, either by systematic differences in data recording or different interpretation of information on exposure or outcome for different patients, reporting as well as selection bias). Besides, prospective studies are prone to bias from loss to follow-up or change in methods over time. To decrease the reporting bias source data verification will be performed in at least 10% of the sites. In order to reduce selection bias, a representative sample of sites will be included in the study. Sites will be selected according to several criteria, main criteria for site selection will be: availability of suitable patients, balanced proportion between clinics and private practices and an equal geographical distribution. Investigators should select patients to be documented in the study only based on eligibility according to inclusion and exclusion criteria, i.e. each patient diagnosed with mCRC and starting treatment for the disease with Stivarga® should be asked for participation in a consecutive manner. No further selection should be applied. Accordingly all patients with mCRC stage IV will be documented in a log file. If the decision has been taken by the physician to treat this patient with Stivarga® the reason for not enrolling the patient in the study has to be documented.

Primary and secondary outcome variables and safety data will be analyzed with regard to different baseline factors. However, unknown and unmeasured risk factors for the outcome variables will exist and might lead to confounding when comparing results in different subgroups and when comparing study results with historical results from clinical studies.

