11.2. Collection

Starting with the first administration of Stivarga®, all non-serious Adverse Events (AE) must be documented on the AE Report Form or to the CRF and forwarded to the sponsor within 7 calendar days of awareness. All serious AEs (SAE) must be documented and forwarded immediately (within 24 hours of awareness).

For each AE/SAE, the investigator must assess and document the seriousness, duration, causal relationship to study drug, action taken and outcome of the event.

If a pregnancy occurs during the study, although it is not a serious adverse event, it should be reported within the same time limits as a serious adverse event. The result of a pregnancy should be followed carefully and any abnormal result of the mother or baby should be reported.

Any AE/SAE occurring up to 30 days after the last intake of Stivarga® has to be documented. However, the documentation of any AE/SAE ends with the completion of the observation period of the patient.

As long as the patient has not received any Stivarga® AEs /SAEs do not need to be documented as such in this non-interventional study. However, they are part of the patient’s medical history.

For any serious drug-related AE occurring more than 30 days after the last intake of Stivarga®, the standard procedures that are in place for spontaneous reporting have to be followed.

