3.1 Does the protocol specify the primary and secondary (if applicable) endpoint(s) to be investigated?				18, 19
3.2 Is the study design described? (e.g. cohort, case-control, randomized controlled trial, new or alternative design)				18
3.3 Does the protocol describe the measure(s) of effect? (e.g. relative risk, odds ratio, deaths per 1000 person-years, absolute risk, excess risk, incidence rate ratio, hazard ratio, number needed to harm (NNH) per year)				27
3.4 Is sample size considered?				26
3.5 Is statistical power calculated?				

Comments:

3.3 absolute risk will be calculated

Section 4: Data sources	Yes	No	N/A	Page Number(s)
4.1 Does the protocol describe the data source(s) used in the study for the ascertainment of:				
4.1.1 Exposure? (e.g. pharmacy dispensing, general practice prescribing, claims data, self-report, face-to-face interview, etc.)				17, 18, 25
4.1.2 Endpoints? (e.g. clinical records, laboratory markers or values, claims data, self-report, patient interview including scales and questionnaires, vital statistics, etc.)				18, 19
4.1.3 Covariates?				22-26
4.2 Does the protocol describe the information available from the data source(s) on:				
4.2.1 Exposure? (e.g. date of dispensing, drug quantity, dose, number of days of supply prescription, daily dosage, prescriber)				25
4.2.2 Endpoints? (e.g. date of occurrence, multiple event, severity measures related to event)				25
4.2.3 Covariates? (e.g. age, sex, clinical and drug use history, co-morbidity, co-medications, life style, etc.)				25

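### Head-count AE percentages cannot be compared between subgroups with different time on drug, and they read too low at the July 2016 interim

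*Protocol*

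**What the plan says.** Section 9.7.5 sets the denominator: "Event rates for single AEs will be calculated based on the total number of patients valid for safety". Section 9.1.2 describes the output in the same terms: "Summary tables will present the number of subjects observed with TEAEs and corresponding percentages". The comment under section 3 of the ENCePP checklist (Annex 2) names the measure: "absolute risk will be calculated". Despite the label of event rates, the planned quantity is therefore an incidence proportion.

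The time over which a patient can contribute an event is not fixed. Under section 9.3.13 new events "will be documented from the first Stivarga[®] intake until 30 days after end of Stivarga[®] treatment". Section 11.2 adds a second limit: "the documentation of any AE/SAE ends with the completion of the observation period of the patient". Section 9.1 leaves treatment duration to the physician alone.

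Two uses of these proportions are announced beyond the overall table. Section 9.7.6 says: "Primary and secondary outcome variables and safety data will be analyzed with regard to different baseline factors". Section 9.7.1 plans two interim analyses that include safety. The first is "one analysis of the baseline and safety data approximately 1.5 years after start of study or after half the patients have been enrolled", whichever is earlier, and the second is in July 2016. Table 1 puts the last patient's first visit at 31 July 2016.

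**The concern.** A patient observed for five weeks counts the same in the denominator as one observed for eight months. That does no harm while the percentage is read as what happened to treated patients over whatever treatment they received. It becomes a problem in two places.

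First, ECOG status, number of prior lines, concomitant diseases and age are named in section 9.7.1 as stratifiers. Such groups may well differ in time on drug. A difference in AE percentages then mixes a difference in tolerability with a difference in length of observation, and a head count cannot separate them.

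Second, at a data cut taken during enrolment or at its end, recently enrolled patients have only just begun their AE window. They are fully in the denominator but have had little time to enter the numerator.

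The study is a post-authorization safety study whose stated reason is that routine patients are more heterogeneous and more comorbid than those of the pivotal trial. The subgroup safety tables are where readers will look for that difference.

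**Working it through.** **The plan's own figures.** The protocol gives no planned AE figure, no expected treatment duration and no AE hazard, so there is nothing on this point to reproduce. Its only numerical plan concerns survival (section 9.5). That reproduces: 0.5^(12/6.4) = 0.273 alive at one year, and 500 × 0.80 × 0.727 = 290.9 deaths, or 292 with the rounded 73%. It does not bear on AEs.

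**Assumptions (mine).** Treatment duration is exponential with median 1.5 to 4 months, so mean m = median/ln 2 = 2.16 to 5.77 months. The AE window is treatment plus 1 month. The hazard h of a first event is constant at 0.05 to 0.20 per month. As an alternative, the event is early: 47% of patients susceptible, mean onset 0.7 month. Enrolment is uniform over 32 months (Q4 2013 to July 2016) with the cut at its end.

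**Step 1: completed windows, constant hazard.** The crude proportion is 1 − e^(−h)/(1 + h·m). At h = 0.10 in every group:

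| Median treatment (months) | m | Crude proportion | Rate per person-month |
|---|---|---|---|
| 1.5 | 2.16 | 25.6% | 0.10 |
| 2 | 2.89 | 29.8% | 0.10 |
| 3 | 4.33 | 36.9% | 0.10 |
| 4 | 5.77 | 42.6% | 0.10 |

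The risk per month is identical, yet the percentages run from 25.6% to 42.6%.

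As a second calibration, take the 46.6% that section 7 cites for hand-foot-skin reaction. Solving for h at mean treatment of 2, 3 and 4 months gives 0.238, 0.185 and 0.152 per month. Halving the mean treatment time at the same h gives 36.3%, 35.0% and 34.1%.

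**Step 2: other event patterns.**
- Early-onset event: 44.3%, 44.8%, 45.4% and 45.8% at median treatment of 1.5, 2, 3 and 4 months. Treatment length hardly matters.
- Toxicity-driven stopping: one group has h = 0.10 and median treatment 3.0 months. The other has h = 0.30, and half of those with an event on treatment stop at it, so median treatment falls to 1.9 months. The crude proportions are 36.9% and 67.8%. The group with the shorter treatment shows the higher percentage. The contrast is still compressed: 67.8/36.9 = 1.8, against a threefold hazard.

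The direction of the subgroup distortion is therefore not fixed.

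**Step 3: the July 2016 interim.** With enrolment over A months, the share of patients with an open window is [1 + m(1 − e^(−(A−1)/m))]/A. The shortfall against the completed-window proportion, for constant h, is

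(1/A) · { (1 − e^(−h))/h − e^(−h)/(1 + hm) + e^(−h) · [hm/(1 + hm)] · [1 − e^(−(h + 1/m)(A−1))]/(h + 1/m) }.

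With A = 32:

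| Median treatment (months) | Open window | Shortfall, h = 0.05 | h = 0.10 | h = 0.20 | Early onset |
|---|---|---|---|---|---|
| 1.5 | 9.9% | 0.9 | 1.5 | 2.2 | 0.8 |
| 2 | 12.1% | 1.4 | 2.2 | 2.9 | 0.9 |
| 3 | 16.6% | 2.5 | 3.6 | 4.2 | 0.9 |
| 4 | 21.1% | 3.7 | 5.0 | 5.3 | 0.9 |

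Shortfalls are in percentage points. Every entry is positive, as it must be, since closing a window can only add events. On the hand-foot-skin calibration (mean treatment 2 to 4 months), 46.6% reads 44.4%, 43.6% and 42.8%.

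**Step 4: the final analysis.** At h = 0.10, with at least 12 months of follow-up for the last patient (section 9.1), at most 2.7% of windows are incomplete and the loss is about 0.1 point. If the Q1 2017 last visit in Table 1 governs, the minimum is about 8 months at the end of that quarter (at most 5.3% incomplete, about 0.6 point). It is about 5 months at the start of the quarter (at most 9.0%, about 1.3 points).

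**The case against.** The strongest reply is that nothing here is an error. Section 9.7.5 leaves further details of the safety analysis to the SAP, and an exposure-adjusted column is ordinary SAP content. The percentage matches the stated measure, absolute risk, and the way the protocol cites the pivotal trial's AE results. Stopping and death are part of that risk in routine use. Section 9.9 warns that AE incidence estimates may be biased, section 9.7.6 warns of confounding between subgroups, and subgroup analyses are exploratory. Treatment duration is summarised separately, and no decision rule hangs on either interim.

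Much of this stands. The percentage is legitimate and should stay, and a person-time measure missing from a protocol is not in itself a fault. But section 9.7.5 does not leave the denominator open. It fixes it, and only further details go to the SAP. The warning on subgroups in section 9.7.6 concerns unknown and unmeasured factors, whereas exposure time is known and measured. Section 9.9 ties variable follow-up to PFS, TTP and DCR, not to AEs.

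A reader might infer something stronger: that subgroups with short treatment will show falsely low AE rates, so that frail patients appear to tolerate the drug better. The documents do not support that. They give no AE timing, no treatment duration and no difference in duration between subgroups, and step 2 shows that the result can be flat or go the other way.

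Nor should the 20% loss in section 9.5 be carried over, since it refers to 12 months of survival follow-up. The first interim was due by Q2 2015 at the latest, before this version of April 2016, so a change now cannot affect its planned report. Finally, the limited window applies to new AE documentation only. Documented events are updated throughout the study, and later serious drug-related events go through spontaneous reporting.

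**Conclusion.** The point holds in a limited form. The AE percentage is a valid description of risk over actual treatment plus 30 days, and the final overall table loses little to incomplete windows: about 0.1 to 0.6 point at h = 0.10, or 1.3 points on the shortest reading of the milestones. It is not a sound basis for comparing baseline subgroups that differ in time on drug. The distortion can be large (25.6% against 42.6% at one and the same constant hazard), negligible, or in the opposite direction.

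At the July 2016 interim the bias has one direction, downward, of roughly 1 to 5 points. The direction does not depend on the assumptions. The size does: exponential treatment with median 1.5 to 4 months, the hazards listed, and uniform enrolment. This is a cheap improvement of low to moderate severity in a descriptive study.

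**What to change.** In section 9.7.5, keep the patient percentages but call them incidence proportions over treatment plus 30 days. For subgroup and interim safety tables, add one of the following for each single AE:

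- first events divided by person-time at risk, counted from first dose to the earliest of first event, last dose plus 30 days, end of observation or data cut-off; or
- cumulative incidence at a fixed time (8 weeks, for example), with death as a competing event and the data cut-off as censoring. The text should also say how a window that closes after treatment stops is handled.

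Base subgroup comparisons on that measure and show exposure beside it. For interim tables, also state how many windows are still open.

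The cost is a sentence or two and extra table columns. Start date, last-dose date and end of observation are already recorded, and AE timing is needed anyway to establish treatment emergence. The drawback of the person-time rate is that it assumes a roughly constant hazard, which early-onset events violate. Fixed-time cumulative incidence avoids this.

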8.2. Secondary objective(s)

Secondary objectives are to determine:

- progression free survival (either clinical progression and/or radiological progression)
- time to progression (either clinical progression and/or radiological progression)
- disease control rate
- duration of Stivarga[®] treatment
- tumor status at different visits
- incidence of treatment emergent adverse events

Additionally possible prognostic factors e.g. presence of severe comorbidities, metastatic sites, early relapse after adjuvant treatment, and KRAS mutation will be evaluated.

9. Research methods

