9.3.4. Co-morbidities (medical history, concomitant diseases)

9.3.4.1 Colon cancer classification

For the classification of colon cancer the following data will be recorded:

- Histology
- Stage (TNM classification)
- Grading (AJCC)
- Anatomical location
- KRAS mutation
- Date of most recent progression/relapse incl. type of assessment

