6.2 Does the protocol discuss the validity of endpoint measurement? (e.g. precision, accuracy, sensitivity, specificity, positive predictive value, prospective or retrospective ascertainment, use of validation sub-study)				

Comments:

--

Section 7: Biases and Effect modifiers	Yes	No	N/A	Page Number(s)
7.1 Does the protocol address:				
7.1.1 Selection biases?				29
7.1.2 Information biases? (e.g. anticipated direction and magnitude of such biases, validation sub-study, use of validation and external data, analytical methods)				29
7.2 Does the protocol address known confounders? (e.g. collection of data on known confounders, methods of controlling for known confounders)				
7.3 Does the protocol address known effect modifiers? (e.g. collection of data on known effect modifiers, anticipated direction of effect)				
7.4 Does the protocol address other limitations?				30

Comments:

--

Section 8: Analysis plan	Yes	No	N/A	Page Number(s)
8.1 Does the plan include measurement of absolute effects?				27, 28
8.2 Is the choice of statistical techniques described?				27, 28
8.3 Are descriptive analyses included?				27, 28

Section 8: Analysis plan	Yes	No	N/A	Page Number(s)
8.4 Are stratified analyses included?				28
8.5 Does the plan describe the methods for identifying:				
8.5.1 Confounders?				
8.5.2 Effect modifiers?				
8.6 Does the plan describe how the analysis will address:				

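### The prognostic-factor objective names only stratified subgroup summaries; no adjustment for the measured baseline factors is planned, so the contrasts can mix their effects

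*Protocol*

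**What the plan says.** The objective is in Protocol section 8.2. After the listed secondary objectives it adds that possible prognostic factors, with severe comorbidities and metastatic sites among the examples, will be looked at: "early relapse after adjuvant treatment, and KRAS mutation will be evaluated".

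Three places describe how:

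- Section 9.7.1: "Whenever reasonable, data will be stratified by subgroups (e.g. primary site of disease, baseline ECOG, number of prior treatment lines, KRAS mutation at study entry", followed by further examples. Early relapse is not among them.
- Section 9.7.5: "Subgroup analyses stratified with prognostic/predictive factors collected at baseline may be explored".
- Section 9.7.6: "Primary and secondary outcome variables and safety data will be analyzed with regard to different baseline factors". This commitment is firm but names no method.

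On confounding, section 9.7.6 says that "unknown and unmeasured risk factors for the outcome variables will exist and might lead to confounding when comparing results in different subgroups". Measured factors are not mentioned. In Annex 2 the item "7.2 Does the protocol address known confounders" is ticked No, and items 8.5.1 and 8.6.1, on identifying and addressing confounding, are ticked not applicable.

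On the data, section 9.3.4.1 lists KRAS mutation and "Date of most recent progression/relapse incl. type of assessment". Section 9.3.4.3 lists prior systemic therapy with best response per regimen. ECOG, metastasis and comorbidities are recorded under sections 9.3.11.1 and 9.3.4.2.

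**The concern.** A statement that a factor is prognostic is normally read as saying that it carries information about outcome beyond the other known factors. A survival curve split by one factor does not show that. The protocol itself expects a heterogeneous population with varied comorbidity (section 7). In such a cohort, performance status, extent of metastasis, comorbidity, number of prior lines and KRAS status are plausibly correlated, and an unadjusted contrast on any one of them then carries part of the others. A factor with no effect of its own can look prognostic, and a real one can be hidden.

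The protocol's caution covers only what it cannot measure. It plans no use of the factors it does measure, and its checklist treats addressing confounding as not applicable. What is at stake is the interpretation of an additional exploratory aim, which is likely to be read alongside the main result.

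Early relapse after adjuvant treatment raises a separate data question. It needs the end of adjuvant therapy and the date of first relapse. Patients enter at third or fourth line (section 9.2.2), so their most recent progression is normally not that first relapse.

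**Working it through.** **1. The protocol's own figures.** From section 9.5: exponential OS, median 6.4 months, 500 patients, 20% loss to follow-up.

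- S(12) = 2^(−12/6.4) = 0.273, so 72.7% die within 12 months.
- Deaths = 500 × 0.80 × 0.727 = 290.9, or 292 with the rounded 73%. The stated 292 is reproduced.
- 95% CI for 1-year survival with n = 400: 0.273 ± 1.96 × √(0.273 × 0.727 / 400) = 22.9% to 31.6%. The stated 23% to 32% is reproduced.

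**2. How far an unadjusted contrast can be off.** The documents give neither the imbalance nor the strength of any factor, so these inputs are assumptions. Factor X has no effect. A recorded confounder C (ECOG, for example) multiplies the hazard by θ and has prevalence p₁ where X is present and p₀ where it is absent. The two groups are of equal size. Survival in group g is

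S_g(t) = (1 − p_g)·e^(−bt) + p_g·e^(−bθt),

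with b set so that the survival curve at the average prevalence has a median of 6.4 months. The crude hazard ratio is the large-sample Cox value with follow-up cut at 12 months. Cells show the crude HR for X, then the group medians in months.

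| θ | 35% v 25% | 45% v 25% | 50% v 20% |
|---|---|---|---|
| 1.5 | 1.04 (6.27 v 6.54) | 1.08 (6.14 v 6.67) | 1.13 (6.02 v 6.81) |
| 2.0 | 1.07 (6.17 v 6.64) | 1.14 (5.95 v 6.89) | 1.22 (5.74 v 7.15) |
| 2.5 | 1.09 (6.09 v 6.73) | 1.19 (5.80 v 7.07) | 1.30 (5.53 v 7.43) |

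Hand check at time zero, where HR = (p₁θ + 1 − p₁)/(p₀θ + 1 − p₀):

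- Mildest corner: (0.35 × 1.5 + 0.65)/(0.25 × 1.5 + 0.75) = 1.175/1.125 = 1.04.
- Strongest corner: (0.50 × 2.5 + 0.50)/(0.20 × 2.5 + 0.80) = 1.75/1.30 = 1.35. This falls to 1.30 over 12 months because high-risk patients die first.

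The distortion runs from negligible to material.

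**3. Whether the data support an adjusted model.** Count parameters as ECOG 2, metastatic sites 2, severe comorbidity 1, KRAS 2 (mutant, wild type, missing), prior lines 1, age 1, sex 1, a total of 10. This coding is an assumption. Then 292/10 = 29 deaths per parameter. Adding early relapse at three levels gives 292/12 = 24.

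Precision for a binary factor at 38% prevalence (the RAS figure in section 7, used as a stand-in): SE(log HR) ≈ 1/√(292 × 0.38 × 0.62) = 0.121, so the 95% limits lie a factor e^(1.96 × 0.121) = 1.27 either side of the estimate. If the other covariates explain 20% of that factor's variance, SE = 0.121/√0.8 = 0.135 and the factor is 1.30. At the strong end of the table, the distortion is therefore as large as the distance from the estimate to its confidence limit.

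**4. Early relapse.** The itemised variables give one relapse date, the most recent. They list prior regimens with best response but no adjuvant intent and no dates. Table 2 adds only general entries for medical history of CRC and previous treatment.

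**The case against.** The best defence is that model specification and derived variables are left to the SAP, which section 9.7.1 says, and that the study is declared descriptive with no hypotheses. Unadjusted survival by subgroup is legitimate description, and section 9.7.6 already cautions about comparing subgroups. The factors in section 8.2 are examples, set apart from the listed secondary objectives.

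Much of this stands. It limits four stronger readings that a reader might be tempted to make:

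- *Factors will be examined only one at a time, or a model is excluded.* The protocol says neither, and section 9.7.6 leaves the method open.
- *Sections 8.2 and 9.7.5 flatly contradict each other.* The wording does weaken from a promise to an option, but the firm sentence in section 9.7.6 stands between them. Both factor lists are introduced as examples, so the absence of early relapse from section 9.7.1 contradicts nothing.
- *Early relapse cannot be derived.* That is true of the itemised list only. The general history entries in Table 2 and the CRF, which is a separate document not shown, may hold regimen intent and dates.
- *Confounding has been shown.* It has not. The hazard ratios above rest on assumed inputs.

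The defence does not remove the point itself. The protocol names a method, states a position on confounding that leaves out every measured factor, and marks the matter as not applicable in its checklist. These are statements in the protocol, not details deferred to the SAP.

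**Conclusion.** The point holds in a limited form. The objective is stated as firm, stratified summaries are the only method named for it (optional in section 9.7.5), and measured confounding is not addressed. Followed as written, the prognostic contrasts would be unadjusted for recorded and plausibly correlated factors.

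The size is unknown. Over confounder hazard ratios of 1.5 to 2.5 and prevalence differences of 10 to 30 percentage points, all assumed, a factor with no effect of its own shows a crude hazard ratio of 1.04 to 1.30. The OS estimate for the whole cohort does not depend on this.

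The early-relapse part is an item to confirm. The protocol does not define the term, and the listed variables do not show how it would be derived. The change is worth making because it is cheap and the planned number of deaths supports it.

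**What to change.** 1. **Section 9.7.5.** Replace the optional sentence with wording such as: *Prognostic factors for OS and PFS will be evaluated in an exploratory multivariable Cox model with baseline ECOG, metastatic sites, severe comorbidity, KRAS (with a missing category), number of prior treatment lines, age and sex; hazard ratios will be given with 95% confidence intervals. Stratified Kaplan-Meier curves are descriptive.* Coding and model checks can stay in the SAP.
2. **Section 9.7.6 and Annex 2.** Name the measured confounders, refer to the model, and correct checklist items 7.2, 8.5.1 and 8.6.1.
3. **Early relapse.** Define it. Confirm that the CRF history captures the end of adjuvant therapy and the first relapse. Code it as early, not early, or no adjuvant therapy. Do not impute it for patients who had no adjuvant therapy, for whom it does not apply. If the dates are not available, remove this factor from the objective.

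The cost is protocol and SAP wording and one extra model; the sample size does not change. Some KRAS or history data will be missing, and a missing category adjusts imperfectly if missingness is related to prognosis. If the CRF lacks the two dates, adding them is not trivial. Enrolment began in Q4 2013 and this version is dated April 2016, so with an assumed median OS of 6.4 months many patients will already have died and the dates would have to come from medical records. That is the reason to allow dropping the factor.
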